#### **Treatment Compliance**

Patient compliance with investigational product will be assessed at each visit by direct questioning and documentation of returned capsules. The number of days where a complete dose was not taken will be recorded and the total number of completed doses missed for each patients will be summarized along with extent of exposure.

Patients who are noncompliant should be discontinued from the study. The number of patients who were withdrawn from the trial for significant non-compliance will be included in the summary of patient status.

## 6.2. Adverse Events

Investigators will monitor the safety of patients and will be responsible for their medical care during the study. The investigator will interpret and document clinically significant signs and symptoms along with any change in conditions and will indicate whether each event is serious or otherwise medically important, considered related to the study medication, or if it caused the patient to discontinue the study medication before completing the study. The patient will be followed until the event resolves, stabilizes with appropriate diagnostic evaluation, or is reasonably explained.

No statistical testing will be performed for comparisons of AEs.

Summaries of AEs will include the number of patients with at least one AE for each treatment group. When reporting by system organ class (SOC) and preferred term (PT), the reports will present the SOC in alphabetical order; while PTs within the SOC will be presented in order of overall decreasing frequency of occurrence in the MP-101 treatment group. A patient with multiple AEs (different PTs) coded to the same SOC will be counted only once for that SOC, but will be counted each time for different PTs within that SOC. A patient with separate events of the same PT (different start/stop dates) will be counted only once in the frequency tables for that PT.

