The most common AEs reported in the 3 clinical studies were (in order of decreasing frequency): dizziness, vomiting, nausea, tiredness, and headache. In the MAD study, vomiting appeared to be a "first-dose" effect for most subjects (1 subject also had an episode of vomiting on Day 2, which did not recur with continued dosing). Nausea also tended to occur during the first 3 days of dosing, whereas dizziness tended to be reported later during dosing and at higher MP-101 doses (150 and 250 mg), but nausea did not persist with ongoing dosing. There were no significant changes in vital signs (blood pressure [BP] and heart rate), electrocardiograms (ECGs; including corrected QT interval [QTc]), and safety laboratory tests (biochemistry, hematology, and urinalysis) in subjects receiving MP-101.

To date, there have been no adverse drug reactions associated with administration of MP-101 in healthy subjects, for which AEs were mild (summarized above). In an elderly patient population with dementia-related psychosis and agitation/aggression, the mild AEs reported in healthy subjects may present a greater safety concern. Adverse events include reports of dizziness which could lead to gait instability and falls in an elderly dementia population. The risk for gait

instability will be assessed for ambulatory patients throughout Study MP-101-01 with the Timed Up and Go (TUG) test. Similarly, transient vomiting, unrelated to the dose, was reported in healthy subjects in the SAD and MAD studies. There is a greater risk of dehydration or aspiration in dementia patients. To improve patient safety, MP-101 exposure will be reduced in Study MP-101-01 (60-mg maximal dose in dementia patients vs. 400-mg QD dose in healthy subjects).

More detailed information about the known and expected benefits, risks, serious adverse events (SAEs), and reasonably anticipated AEs of MP-101 can be found in the Investigator's Brochure (IB).

4. Objectives and Endpoints

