7.4. Dose Titration

Figure 7.1 illustrates the dose titration schedule.

[figure not shown]

Figure 7.1. Dose titration schedule for protocol MP-101-01.

At Visit 2 (Week 0), patients will be randomized to the MP-101 arm or the placebo arm. All patients will start at a dose of 20 mg or equivalent placebo (Figure 7.1). If intolerance is reported at a dose of 20 mg between Visit 2 (Week 0) and Visit 3 (Week 1), the patient will be discontinued from the study. Intolerance is defined as the inability to tolerate TEAEs such as dizziness, nausea, and vomiting, which in the opinion of the investigator are possibly related to MP-101.

At Visit 3 (Week 1), the dose of MP-101 (or equivalent placebo) will be increased to 40 mg. If intolerance is reported at a dose of 40 mg between Visit 3 (Week 1) and Visit 4 (Week 2), the patient will be discontinued from the study.

At Visit 4 (Week 2), the dose of MP-101 (or equivalent placebo) will be increased to 60 mg. If intolerance is reported at a dose of 60 mg between Visits 4 (Week 2) and 5 (Week 4), the patient will be asked to return for an unscheduled visit for down-titration to 40 mg. Patients down-titrated to 40 mg prior to Visit 5 (Week 4) will remain at this dose for the remainder of the study.

At Visit 5 (Week 4), the dose of MP-101 (or equivalent placebo) will be maintained at 60 mg. If intolerance is reported at a dose of 60 mg at Visit 5 (Week 4), the patient will be down-titrated to 40 mg and will remain at this dose for the remainder of the study. If intolerance is reported at a dose of either 40 mg or 60 mg beyond Visit 5 (Week 4), the subject will be discontinued from the study.

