9.2.1. Serious Adverse Events

An SAE is any AE from this study that results in 1 of the following outcomes:

- death
- initial or prolonged inpatient hospitalization
- considered life-threatening
- persistent or significant disability/incapacity
- congenital anomaly/birth defect
- considered significant by the investigator for any other reason: important medical events that may not result in death, be life-threatening, or require hospitalization may be considered serious based on best medical judgment

Study site personnel must alert Mediti Pharma, Inc., or its designee, of any SAE within 24 hours of investigator awareness of the event via a sponsor-approved method. If alerts are issued via telephone, they are to be immediately followed with official notification on study-specific SAE forms. This 24-hour notification requirement refers to the initial SAE information and all follow-up SAE information.

As with AEs, SAE reporting begins after the patient has signed informed consent.

Investigators are not obligated to actively seek AEs or SAEs in patients once they have discontinued from and/or completed the study (the patient summary CRF has been completed). However, if the investigator learns of any SAE, including a death, at any time after a patient has been discharged from the study, and he/she considers the event reasonably possibly related to the study treatment or study participation, the investigator must promptly notify Mediti Pharma, Inc. or its designee.

Pregnancy (maternal or paternal exposure to investigational product) does not meet the definition of an AE. However, to fulfill regulatory requirements any pregnancy should be reported following the SAE process to collect data on the outcome for both mother and fetus.

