## **1.4.** Sample Size Determination

Approximately 100 patients will be enrolled to enable approximately 80 evaluable patients to complete the study through at least Visit 5 (Week 4).

The primary analysis will use a one-sided Fisher's exact test with a 5% type 1 error rate.

If the NPI response rate in MP-101 treated patients is 30% greater than in placebo treated patients (65% vs 35%), with 40 evaluable patients per treatment group there is at least an 80% chance (i.e. Power) that MP-101 will demonstrate superiority to placebo.

The sample size was calculated assuming an expected 20% drop-out rate of patients in each arm prior to Week 4, so that 100 patients are planned to be enrolled to arrive at 40 patients/arm (N=80) in the Evaluable population.

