## 6. SAFETY ANALYSES

All analyses of safety including the extent of exposure to study medication will be performed using the Safety population.

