#### **Treatment-Emergent Adverse Events**

Treatment-emergent adverse events (TEAE) include all adverse events that emerge or worsen after taking the first dose of study drug. TEAEs will be summarized for each treatment group by SOC and PT, and by PT in order of decreasing frequency of MP-101 preferred term.

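### Adverse events are reported only as crude percentages of all dosed patients, so unequal study exit could under-count later-onset events; by-period and time-at-risk tables beside them are a cheap improvement

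*SAP*

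**What the plan says.** **Measure and denominator.** SAP 6.2: "Summaries of AEs will include the number of patients with at least one AE for each treatment group". The same section adds: "No statistical testing will be performed for comparisons of AEs". The denominator comes from SAP 6: "All analyses of safety including the extent of exposure to study medication will be performed using the Safety population". The definition of treatment-emergent events sets a start but no end: "Treatment-emergent adverse events (TEAE) include all adverse events that emerge or worsen after taking the first dose of study drug". The special-interest table (dizziness, nausea, vomiting) adds event totals but no time at risk.

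**Exit rules.** Under Protocol 7.4, if a patient does not tolerate 20 mg in the first week, "the patient will be discontinued from the study. Intolerance is defined as the inability to tolerate TEAEs such as dizziness, nausea, and vomiting". Study exit also follows intolerance at 40 mg between Weeks 1 and 2, and at either dose after Visit 5. Intolerance at 60 mg between Week 2 and Visit 5, or at Visit 5, leads to down-titration. Placebo follows matching rules.

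**Collection after exit.** Protocol 9.2.1: "Investigators are not obligated to actively seek AEs or SAEs in patients once they have discontinued from and/or completed the study". Some collection continues. Protocol 8.2 provides for an early termination visit, although failure to return is not a deviation. Protocol 9.2 requires follow-up of existing events that are serious, related or caused drug discontinuation. Later serious events judged related must be reported. Completers are seen at Visit 9, Day 77.

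**Planned loss.** SAP 1.4 sizes the trial "assuming an expected 20% drop-out rate of patients in each arm prior to Week 4". Protocol 10.3.1 adds that withdrawal is taken to be unrelated to the treatment effect.

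**The concern.** Tolerability is a secondary objective and treatment-emergent events are its main endpoint. With no testing planned, the descriptive tables carry the conclusion.

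A crude percentage over all dosed patients gives a patient who left in Week 1 the same weight as one watched for 11 weeks. Two effects follow.

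- Patients who leave at 20 or 40 mg never take 60 mg, yet they stay in the denominator for events that arise at 60 mg. This dilutes the percentage in both arms, even when exit is equal.
- If one arm loses more patients, its later events are under-counted relative to the other arm. A real excess can look smaller, or an equal risk can look unequal.

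The under-count concerns later events of a kind other than the one that caused exit. The event that caused exit is itself counted.

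**Working it through.** **The plan's own figure.** 80 evaluable / (1 − 0.20) = 100 enrolled, as stated, so about 50 per arm at 1:1. The documents give no adverse event rate and no exit rate that differs by arm. The event risks, the split of exits and the exit times below are therefore assumptions.

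**Step 1: share of the observation window kept.** A completer's window is 77 days (Protocol Section 2). If a fraction *d* leaves on day *t*, the share kept is (1 − *d*) + *d* × *t*/77.

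- *d* = 0.20: 0.818 at Day 7, 0.836 at Day 14, 0.873 at Day 28. The plan's own loss rate therefore costs 13% to 18% of an arm's window.
- 25% and 15% exit at Day 14: 0.795 and 0.877, ratio 0.91.
- 30% and 10% exit at Day 14: 0.755 and 0.918, ratio 0.82.

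**Step 2: a later event unrelated to exit, with equal true risk.** Take a 20% risk between Week 2 and Week 11 in both arms, exits at Week 2, and nothing observed afterwards. Crude percentage = 20% × (1 − *d*).

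| Exit, arm A / arm B | Crude, A / B | Ratio |
|---|---|---|
| 20% / 20% | 16% / 16% | 1.00 |
| 25% / 15% | 15% / 17% | 0.88 |
| 30% / 10% | 14% / 18% | 0.78 |
| 35% / 5% | 13% / 19% | 0.68 |
| 40% / 10% | 12% / 18% | 0.67 |

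If the 30% and 10% exits come at Week 4 instead, with a constant hazard, the result is 15.5% and 18.5% (ratio 0.84).

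**Step 3: a true doubling, 20% against 10%.**

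- Exit 20% in both arms at Week 2: 20% × 0.80 = 16% and 10% × 0.80 = 8%. The ratio stays at 2.0 and the difference falls from 10 to 8 points.
- Exit 30% in the higher-risk arm and 10% in the other: 20% × 0.70 = 14% and 10% × 0.90 = 9%. The ratio falls to 1.56 and the difference to 5 points.

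If the lower-risk arm loses more patients, the bias runs the other way.

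**Step 4: what the added tables would show.** Take the 30% / 10% row of Step 2 with 50 per arm. There are 7 events among the 35 patients still observed and 9 among the 45. By period this is 7/35 = 20% and 9/45 = 20%. By time at risk it is 7/282 and 9/363 patient-weeks, or 2.48 per 100 patient-weeks in each arm.

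**Step 5: scale against chance.** The crude counts of 7 and 9 of 50 differ by 4 points. The standard error of that difference is √(0.14 × 0.86/50 + 0.18 × 0.82/50) = 0.073, or 7.3 points. The distortion is systematic but smaller than the chance variation in a trial of this size.

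**The case against.** **The direction is not established.** A reader might infer that MP-101 will lose more patients, because intolerance is described by effects already seen with the drug. That is plausible, but the documents do not show it. The plan assumes 20% in each arm, and Protocol 7.7 withdraws patients who need rescue therapy, which could remove more placebo patients. This objection stands.

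**Late dizziness is weak evidence here.** Protocol Section 3 says that "dizziness tended to be reported later during dosing and at higher MP-101 doses", and it names 150 and 250 mg, in healthy subjects dosed for up to 14 days. This trial's maximum is 60 mg. Exposure narrows the gap for some patients: scaling the 400 mg maximum concentration in Protocol 5.5 by dose gives 10900 × 150/400 ≈ 4090 nM at 150 mg, inside the 2800 to 4800 nM interval predicted for 60 mg at an eGFR of 45. This still does not show onset after Week 2.

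**The dizziness row may not be under-counted.** A reader might apply Step 2 to dizziness and infer a false advantage for the arm losing more patients. But dizziness that causes exit is already in that row. If half of the 20-point excess exit were due to dizziness (an assumption), the row would read 14% + 10% = 24% against 18%. For the same reason the count of patients with any event hardly moves. This objection stands and limits the point to other later-onset events.

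**Exit is neither universal nor the end of all collection.** Down-titration and the continuing collection described above both count. Protocol 8.1.1 also asks sites to attempt scheduled procedures after drug is stopped, but the titration rule is exit from the study, which 8.2 governs. New non-serious events after the early termination visit remain unsought.

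**Imbalance would be partly visible.** SAP 6.1 summarizes dosing duration and maximum dose, SAP 4.1 covers last visit and reasons for leaving, and SAP 6.6 gives the Timed Up and Go result by visit. These would reveal unequal exposure, but none relates events to time at risk.

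**At-risk tables have their own bias.** Later periods hold only patients who tolerated earlier doses, and exit for intolerance is informative. This stands, and is why the tables should supplement the crude ones.

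**Conclusion.** The point holds as a cheap improvement. The plan has no adverse event display by dosing period or time at risk, although most intolerance leads to study exit and active collection then largely stops.

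For later events unrelated to exit, exits that differ by 10 to 30 percentage points at Week 2 would give a crude ratio of 0.88 to 0.67 when the true ratio is 1. With equal exit there is no bias in the ratio, only a smaller absolute difference. These figures rest on assumed exit splits and event risks, exit at one time point, and no observation after exit.

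The documents do not support the stronger conclusion that the tables will make MP-101 look safer than it is. That would require more exits on MP-101 and late events distinct from those that caused exit, and neither is established. The primary analysis and the sample size are unaffected.

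**What to change.** Keep the crude tables in SAP 6.2. For the special-interest events and the common treatment-emergent events, add:

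- **(a)** incidence by arm and period (Weeks 0–2, 2–4, 4–10, follow-up), with patients still under observation at the start of each period as the denominator;
- **(b)** exposure-adjusted incidence, or cumulative incidence of first event by arm, with study exit for intolerance handled as a competing event and not as non-informative censoring.

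The competing-event curve will end close to the crude percentage. Its use is to show when events and exits occurred. Table (a) and the exposure-adjusted rate are what correct for unequal observation, and only as far as those who left resemble those who stayed. Read all of them beside the crude tables, not in place of them.

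Time at risk should come from dosing, visit and event dates. The cumulative dose in SAP 6.1 should not be used for this: with three capsules a day its weights give 20 × 1/3 × 3 = 20, 40 × 2/3 × 3 = 80 and 60 × 3 = 180 mg per full day at the 20, 40 and 60 mg levels, so that formula and the stated doses must be reconciled.

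**Cost.** SAP wording and one or two tables from dates already collected, with no change to conduct or sample size. Later denominators will be smaller and made up of patients who tolerated the earlier doses, which a footnote should say.

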#### **Treatment-Emergent Adverse Events**

Treatment-emergent adverse events (TEAE) include all adverse events that emerge or worsen after taking the first dose of study drug. TEAEs will be summarized for each treatment group by SOC and PT, and by PT in order of decreasing frequency of MP-101 preferred term.

#### **Serious Adverse Events**

Treatment-Emergent SAEs will be summarized for each treatment arm by SOC and PT. These reports will also include the total number of SAE for each SOC and PT.

#### Treatment-Emergent Adverse Events Resulting in Death

If there are any TEAEs that result in death, a listing of all deaths will be provided. In addition, a summary table may also be created by PT in order of decreasing frequency of MP-101 preferred term.

#### **Treatment-Emergent Adverse Events Leading to Study Discontinuation**

TEAEs for which the action taken with medication is 'Drug Withdrawal' will be identified as TEAEs that lead to study discontinuation. The TEAEs that lead to study drug discontinuation will be summarized for each treatment group by SOC and PT for the Safety population. A by-patient listing of the TEAEs that lead to study drug discontinuation will also be provided.

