7.2.1. Timing of Dose Administration

The dose will be administered at approximately the same time in the morning each day. Patients will record the actual time of each dose of study drug and the time of food consumption before and after each dose; this information will be collected.

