## 6.1. Study Medication Exposure and Treatment Compliance

#### **Extent of Exposure**

Patient exposure to study drug will be summarized by the duration of dose administration, the cumulative total dose while in the trial, and the maximum dose taken.

Study drug is administered on site at each visit the dose level is changed, except Visit 2. The last dose will be assumed to have been administered on the day before each drug accountability visit. Therefore, duration of dosing will be calculated as the numbers of days (inclusive) between the first day study drug was taken and the last day study drug was taken. Missing start or end dates will not be imputed.

MP-101 will be provided in a wallet design (blister pack) containing blister strips. Blister packs will be dispensed at Visits 2, 4, 5, and 6 (Weeks 0, 2, 4, and 6, respectively). Each wallet will contain 9 rows of 3 capsules each. For the 20mg active dose, each row contains 1 capsule of active drug and 2 placebo capsules. For the 40mg active dose, each row contains 2 capsules of active drug and 1 placebo capsule. For the 60mg active dose, each row contains 3 capsules of active drug. For patients in the placebo arm, all capsules contain placebo.

The number of capsules taken will be assumed to be 27 times the number of kits dispensed minus the number of capsules returned. For patients while on the 20mg and 40mg dose levels, it will not be possible to know how many active drug capsules were consumed if only partial doses were taken. Therefore, the cumulative total dose taken will be approximated as:

- 20\*(1/3)\*(number of capsules taken while at the 20mg dose level) +
- 40\*(2/3)\*(number of capsules taken while at the 40mg dose level) +

60\*(number of capsules taken while at the 60mg dose level)

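### No planned SAP summary identifies or counts patients down-titrated from 60 mg to 40 mg, and two exposure rules in SAP 6.1 need repair

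*SAP*

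**What the plan says.** **Routing of intolerance (Protocol 7.4, repeated in SAP 2.4).** Intolerance at 20 mg or 40 mg before Visit 4 leads to discontinuation. At 60 mg between Visit 4 (Week 2) and Visit 5 (Week 4), "the patient will be asked to return for an unscheduled visit for down-titration to 40 mg", and "Patients down-titrated to 40 mg prior to Visit 5 (Week 4) will remain at this dose for the remainder of the study". Intolerance to 60 mg reported at Visit 5 also leads to 40 mg. After Visit 5, intolerance at either dose leads to discontinuation. The Protocol synopsis applies similar rules to placebo, to keep the blind.

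**Adverse events (SAP 6.2).** One table depends on action taken: "TEAEs for which the action taken with medication is 'Drug Withdrawal' will be identified as TEAEs that lead to study discontinuation". The other treatment-emergent tables (all events, drug-related, by maximal severity, common non-serious, special interest) ignore action taken.

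**Exposure (SAP 6.1).** Exposure is described by "the duration of dose administration, the cumulative total dose while in the trial, and the maximum dose taken". Each row of three capsules holds one, two or three active capsules at 20, 40 and 60 mg. The cumulative-dose formula credits 20×(1/3), 40×(2/3) and 60 mg per capsule at those levels.

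**Last dose (SAP 6.1).** "The last dose will be assumed to have been administered on the day before each drug accountability visit". The next sentence defines duration by the first and last days on which drug was taken and says that missing dates are not imputed. Protocol 7.2.1 states: "Patients will record the actual time of each dose of study drug".

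**The concern.** The protocol handles one clinical judgement, intolerance, by two routes according to timing and dose. The SAP labels and tabulates only the discontinuation route. SAP 2.6 brings unscheduled visits into the summaries through clinically significant findings or withdrawal, and SAP 4.1 tabulates reasons for study discontinuation. A patient stepped down to 40 mg who completes the study is in neither the withdrawal table nor the discontinuation reasons.

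Tolerability is in the study title and is a secondary objective, and Protocol 5.4 frames the hypothesis around a 60 mg target dose. Whether patients can stay on 60 mg is therefore a basic output of this Phase 2 trial. As specified, withdrawals and maximum dose could look alike in the two arms while down-titration differed. The primary analyses group patients by arm whatever their final dose, so they would not show it either.

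**Working it through.** The documents give no down-titration rate and no expected exposure, so there is no stated figure to reproduce. The check applies the SAP 6.1 measures to example patients.

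**Inputs.** Protocol Table 7.1 gives 7 days at 20 mg, 7 days at 40 mg, then 60 mg. Assumed: full compliance and 70 dosing days (Days 0–69). Down-titrated patients switch to 40 mg from Day 15 at the earliest or Day 28 (Visit 5) at the latest, and complete.

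**Actual cumulative dose** = 20×d20 + 40×d40 + 60×d60, where d is days at each level.
- Completer on 60 mg: 20×7 + 40×7 + 60×56 = 3,780 mg.
- Switched from Day 15: 20×7 + 40×62 + 60×1 = 2,680 mg (71%).
- Switched from Day 28: 20×7 + 40×49 + 60×14 = 2,940 mg (78%).

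**Formula as written in SAP 6.1**, with three capsules a day. Per day it credits 20 mg at the 20 mg level, 3×40×(2/3) = 80 mg at the 40 mg level, and 3×60 = 180 mg at the 60 mg level.
- Completer: 140 + 7×80 + 56×180 = 10,780 mg.
- Switched from Day 15: 140 + 62×80 + 1×180 = 5,280 mg (49%).
- Switched from Day 28: 140 + 49×80 + 14×180 = 6,580 mg (61%).

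| Measure | Completer on 60 mg | Down-titrated, Day 15 to Day 28 |
|---|---|---|
| Maximum dose | 60 mg | 60 mg |
| Duration | 70 days | 70 days |
| Actual cumulative dose | 3,780 mg | 2,680–2,940 mg |
| SAP formula | 10,780 mg | 5,280–6,580 mg |

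Maximum dose and duration do not respond at all. Cumulative dose does, but it does not identify the cause. A patient on 60 mg who stops early reaches the same total after 14 + (2,680 − 420)/60 = 51.7 to 14 + (2,940 − 420)/60 = 56 dosing days. An arm mean also dilutes the signal. If 10 of 50 completers switched from Day 21 (2,800 mg each), the mean would be (10×2,800 + 40×3,780)/50 = 3,584 mg, 5% below 3,780.

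**Capsule check.** Average active content per capsule is 20×(1/3) = 6.7 mg, 20×(2/3) = 13.3 mg and 20×(3/3) = 20 mg. The formula credits 6.7, 26.7 and 60 mg, so only the first term is right. The others are too large by factors of 2 and 3, which turns a true 22–29% shortfall into an apparent 39–51%.

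**Last dose.** With an early-termination visit on day E and a true last dose on day L, the day-before rule counts E days (Days 0 to E−1) against L+1 true days. For illustration, take L = 17 and E = 24: 24 days against 18, or +33%. Conversely, Protocol Table 9.1 samples Visit 8 at 2 to 4 hours postdose, so a dose that day is expected. A completer dosed on Day 70 has 71 days and is counted as 70.

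**The case against.** The strongest reply is that the events are not lost. Protocol 7.4 defines intolerance through events such as dizziness, nausea and vomiting, and SAP 6.2 tabulates all treatment-emergent events by arm, with a dedicated special-interest table for those three categories. A reader might infer that intolerance in Weeks 2–4 appears in no tolerability or exposure summary. The documents do not support that: the events are counted and cumulative dose falls. What is missing is the link to the dose reduction.

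A reader might also infer that nothing else planned would reveal it. That too is unsupported, because the PK–QTcF figures in SAP 7 mark the dose level at each assessment. They are plots without counts, however, and Protocol 9.5.2 plans to assay only MP-101 patients, so they give no comparison between arms.

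Nor do the documents show that symptoms cluster at the step to 60 mg. Protocol Section 3 reports "Nausea also tended to occur during the first 3 days of dosing" and describes vomiting as mainly a first-dose effect. In this trial the first dose is 20 mg, where intolerance leads to discontinuation, and Protocol 5.5 says titration is meant to limit nausea and vomiting.

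A further reading, that every patient would show a 60 mg maximum, holds only for those who reach that step. Exposure uses the Safety population, so patients who stop at 20 or 40 mg show lower maxima.

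On duration, the sentence after the day-before rule can be read as using actual dates, and Table 7.1 lists dosing only through Week 9. The text is ambiguous rather than plainly wrong. The Day 17 example fits a patient who stops for a reason other than intolerance at 60 mg, since Protocol 7.4 would route that intolerance to 40 mg.

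Finally, table formats sit in a companion document and variable values in the eCRF, neither available here, and SAP 1.1 allows extra supportive analyses without amendment. This stands, and it makes the gap modest. It does not supply the missing count.

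**Conclusion.** The point holds as a reporting gap: no summary described in the SAP identifies or counts, by arm, patients whose intolerance of 60 mg was managed by down-titration. The general adverse-event tables show that symptoms occurred, and cumulative dose shows less drug taken. Neither shows that the patient could not remain on the target dose.

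The number affected cannot be derived from the documents. Purely as an assumption, if 45 patients per arm reach Visit 4 and 10–30% on MP-101 against 5% on placebo are down-titrated, that is 4.5–13.5 against about 2.3 patients. These patients would not be separately identified; their events would not be missing.

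The formula error is definite. On the SAP's own capsule contents it credits 10,780 mg to a compliant 70-day completer who took 3,780 mg. The last-dose rule is a smaller, conditional fault: one day for completers dosed on the day of Visit 8, and a variable overstatement for patients who stopped well before an accountability visit. It depends on how the two adjacent SAP sentences are meant to fit together.

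None of this touches the primary test or its power. The change should be made because tolerability is an objective and the repair is cheap.

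**What to change.** - **SAP 6.2:** add a table of treatment-emergent events leading to dose reduction, by arm, separate from those leading to drug withdrawal.
- **SAP 6.1, dose attained:** keep maximum dose and add n (%) by arm who reached 60 mg, were down-titrated to 40 mg (including at Visit 5), and were on 60 mg at last dose.
- **SAP 6.1, last dose:** take the date from recorded dosing data (dose times under Protocol 7.2.1, the diary under 7.6, and the two most recent doses under 9.5.1). Use the day-before rule only where no date is recorded, and say how it relates to the last day on which drug was taken.
- **SAP 6.1, cumulative dose:** make the multipliers match the capsule contents, i.e. 20×(1/3), 20×(2/3) and 20 mg per capsule at the three levels.

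The cost is a little programming. Dose level is already needed for the cumulative dose and the PK figures. Whether the eCRF action-taken field has a dose-reduction value should be confirmed; if it does not, dispensing and dose-level records can identify the patients. Titration rules, sample size and alpha are unchanged.
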